## **6 STUDY PERIODS, TREATMENT REGIMENS AND POPULATIONS FOR ANALYSES**

### **6.1 Study Periods**

#### **6.1.1 Baseline Period**

Baseline evaluations or events will be defined as evaluations or events that occur before the date and time of the first dose of study treatment.

In cases where the time (onset time of event or evaluation time and dosing time) is missing or not collected, the following definition will apply:

- Pre-treatment AEs will be defined as AEs with an onset date prior to but not including the day of the first dose of study treatment
- Baseline evaluations (laboratory tests, pulse oximetry and vital signs) will be defined as evaluations with a date on or prior to the day of first dose of study treatment

If there are multiple valid assessments, the assessment that is closest to day (and time if collected) of the first dose of study treatment will be used as the baseline in the analyses. If multiple assessments are collected at the same date (and time if collected), the assessment with the latest database entry date (and time if collected) will be considered as baseline.

#### **6.1.2 Post Baseline Period**

On-treatment AEs will be defined as AEs with an onset date and time on or after the date and time of the first dose of study treatment (or with an onset date on or after the day of first dose of study treatment if time is not collected or is missing). An AE will be counted as on-treatment if the event occurred within 30/100 days of the last dose of study treatment.

On-treatment evaluations (laboratory tests, pulse oximetry, and vital signs) will be defined as evaluations taken after the day (and time, if collected and not missing) of first dose of study treatment. An evaluation will be counted as on-treatment if it occurred within 30/100 days of the last dose of study treatment.

### **6.2 Treatment Regimens**

The treatment group “**as assigned**” will be retrieved from the IVRS system.

The treatment group “**as treated**” will be the same as the arm as assigned by IVRS. However, if a subject received the incorrect drug for **the entire period** of treatment the subject’s treatment group will be defined as the incorrect drug the subject actually received.

### **6.3 Populations for Analyses**

As noted previously, this SAP describes analyses for the SCLC expansion cohort as well as the SCLC pooled pre-expansion and expansion cohorts; therefore, for the descriptions provided below, “subjects” refers to “subjects with SCLC - Expansion Cohort” and “subjects with SCLC” where applicable.

- All Enrolled Subjects: All subjects who signed an informed consent form and were registered into the IVRS.
- All Randomized Subjects: All subjects who were randomized to any treatment arm in the SCLC Expansion Cohort.
- All Treated Subjects: All subjects who received at least one dose of any study medication.
- All Response Evaluable Subjects: A subject will be part of the response evaluable subject if the following criteria are met:
  - a) BOR is in (CR, PR, PD or SD),
  - b) at least one target lesion identified at baseline,
  - c) at least one on-study timepoint with target lesion assessment (non missing percent change from baseline).
- All PK Subjects: All assigned subjects with available serum time-concentration data.
- All Immunogenicity Subjects: All treated subjects with baseline and at least 1 post baseline immunogenicity assessment.
- All PD-L1 Tested Subjects: All subjects who had a tumor tissue sample available for assessment of PD-L1 expression at baseline.
- All Treated, PD-L1 Tested Subjects: All PD-L1 tested subjects who received at least one dose of study treatment.
- PD-L1 Evaluable Subjects: All treated, PD-L1 tested subjects with quantifiable PD-L1 expression.

## 7 STATISTICAL ANALYSES

### 7.1 General Methods

Unless otherwise noted, analyses outlined in [Sections 7.2](#) through [7.5](#) and [Section 7.9](#) will be performed using the SCLC expansion cohort treated with nivolumab monotherapy or with nivolumab in combination with ipilimumab (nivolumab 1 mg/kg + ipilimumab 3 mg/kg). Safety will be summarized for all treated subjects in the SCLC pooled pre-expansion and expansion cohorts, by treatment group (nivolumab and nivolumab 1 mg/kg + ipilimumab 3 mg/kg). All listings will be produced for the SCLC pooled pre-expansion and expansion cohorts.

The following subsections describe tabulations of discrete variables, by the frequency and proportion of subjects falling into each category, for the SCLC expansion cohort. Percentages given in these tables will be rounded and, therefore, may not always sum to 100%. Continuous variables will be summarized for the expansion cohort using the mean, standard deviation, median, minimum and maximum values.

Time to event distributions (i.e. overall survival, progression free survival, time to response, and duration of response) will be estimated using Kaplan Meier techniques. When appropriate, the

median along with 95% CI will be provided using Brookmeyer and Crowley methodology (using the log-log transformation for construction of confidence intervals). Rates at fixed timepoints (e.g. OS at 12 months) will be derived from the Kaplan Meier estimate along with their corresponding log-log transformed 95% confidence intervals. Confidence intervals for binomial proportions will be derived using the Clopper-Pearson method.

## **7.2 Study Conduct**

### **7.2.1 Accrual**

The following will be presented on the enrolled population for all treatment groups:

- Number of subjects accrued by country and investigational site
- Number of subjects accrued by month

### **7.2.2 Relevant Protocol Deviations**

The following programmable deviations will be considered as relevant protocol deviations and summarized for the SCLC expansion cohort (including nivolumab and nivolumab 1 mg/kg + ipilimumab 3 mg/kg treatment groups). Non-programmable relevant eligibility and on-treatment deviations, as well as significant (both programmable and non-programmable) eligibility and on-treatment protocol deviations will be reported through ClinSIGHT listings.

#### At Entrance:

- Subjects with baseline ECOG performance status > 1
- Subjects without measurable disease at baseline

#### On-study:

- Subjects receiving anti-cancer therapy (chemotherapy, radiotherapy, hormonal therapy, immunotherapy, standard or investigational agents for treatment of cancer) while on study therapy.
- Subjects treated differently than as assigned (subjects who received the wrong treatment, excluding the never treated).

Listings will also be provided.

## **7.3 Study Population**

### **7.3.1 Subject Disposition**

The total number of subjects enrolled (assigned or not assigned) will be presented along with the reason for not being assigned. This analysis will be performed on the all enrolled population only.

Number of subjects who discontinued study treatment along with the corresponding reason will be tabulated by treatment group as treated. Reason for discontinuation will be derived from subject status CRF page. This analysis will be performed only on the All Treated Subjects population.

Number of subjects randomized but not treated along with the reason, will be tabulated by treated group as assigned. This analysis will be performed on the All Randomized Subjects population.

A subject listing for All Treated Subjects will be provided showing the subject's first and last dosing date, off study date and reason for going off-study.

### 7.3.2 **Demographics and Baseline Characteristics**

The following baseline characteristics will be summarized for all treated subjects by treatment group for the expansion cohort. All baseline presentations identify subjects with missing measurements. In tabulations of categorical variables, percent is based on subjects with measurements. Listings will also be provided.

- Age (descriptive statistics)
- Age category (< 65, ≥ 65 - < 75, ≥ 75, ≥ 65)
- Gender (male/female)
- Race (white/black/asian/other)
- Ethnicity (Hispanic or Latino/Not Hispanic or Latino)
- Region (US, Europe, Rest of World)
- Number of Prior Lines of Therapy (0, 1, 2-3, 4-5, >5)
- ECOG Performance Status (0/1)
- Weight (descriptive statistics)
- Baseline LDH (≤ULN, >ULN)
- Baseline LDH (≤2\*ULN, >2\*ULN)
- History of brain metastases (yes/no)
- Baseline liver metastases (yes/no)
- Baseline visceral metastases (lung, liver and bone) (yes/no)
- Baseline lymph node only (yes/no)
- Baseline hemoglobin (< 10g/dL vs. ≥ 10g/dL)
- Baseline creatinine clearance (CrCL) (< 30, 30 - < 60, ≥ 60 ml/min)

The creatinine clearance will be calculated using Cockcroft-Gault formula, defined as:

Formula 1 (for males):

$$CrCL(ml/min) = \frac{(140 - age(in\ years)) * weight(in\ kg)}{72 * serum\ creatinine(in\ mg/dL)}$$

or Formula 2 (for females):

$$CrCL(ml/min) = \frac{(140 - age(in\ years)) * weight(in\ kg)}{72 * serum\ creatinine(in\ mg/dL)} * 0.85$$

Baseline weight will be used.

- Time from Initial Disease Diagnosis to Assignment (<1 year, , ≥2 years)

- Platinum resistant/refractory versus platinum sensitive based on the prior systemic cancer therapy
- Smoking status

### **7.3.3 Medical History**

General medical history will be listed by subject.

### **7.3.4 Prior Therapy**

The following will be summarized for the expansion cohort (nivolumab and nivolumab 1 mg/kg + Ipilimumab 3 mg/kg treatment groups):

- Prior neo-adjuvant therapy (yes/no)
- Prior adjuvant therapy (yes/no)
- Time from completion of prior adjuvant therapy to assignment (subjects who received prior adjuvant therapy), (< 6 months and  $\geq$  6 months)
- Prior surgery related to cancer (yes/no)
- Prior radiotherapy (yes/no)
- Number of prior therapies received (1, 2, 3,  $\geq$ 4)
- Best response to most recent prior regimen (CR/PR vs SD vs PD)
- Time from first line treatment to start of second line treatment ( $\leq$  90 days and > 90 days)
- Prior platinum experience (cisplatin only, carboplatin only, both or other) by setting
- Time from completion of most recent prior regimen to study treatment (< 3, 3- < 6,  $\geq$  6 months)

Agents and medication will be reported using the generic name. A listing by subject will also be provided.

### **7.3.5 Baseline Examinations**

Subjects with abnormal baseline physical examination will be tabulated by examination criteria for the expansion cohort (nivolumab and nivolumab 1 mg/kg + ipilimumab 3 mg/kg treatment groups). A by-subject listing will accompany the table.

## **7.4 Extent of Exposure**

Analyses in this section will be performed for the expansion cohort (nivolumab and nivolumab 1 mg/kg + ipilimumab 3 mg/kg treatment groups).

For the analyses of crossover subjects during original assigned treatments, the exposure will be truncated at the first crossover dose date. All others will follow regular counting rules.

### **7.4.1 Administration of Study Therapy**

The following parameters will be summarized (descriptive statistics) by treatment group (refer to [Table 7.4.1-1](#)):

- Relative dose intensity (%) using the following categories: <50%, 50 - <70%; 70 - <90%; 90 - <110%; ≥110%
- Number of doses of nivolumab, ipilimumab (summary statistics)
- Duration of treatment: duration of treatment will be presented using a Kaplan-Meier curve whereby the last dose date will be the event date for those subjects who are off study therapy. Median duration of treatment and associated 95% CI will be provided. Subjects who are still on study therapy will be censored on their last dose date.
- A by-subject listing of extent of exposure (weight, number of doses, date of first and last dose, cumulative dose, relative dose intensity, duration of treatment, and reason for discontinuation) and a listing of batch number will be provided.

**Table 7.4.1-1: Study Therapy Parameter Definitions**

	Nivolumab in Arm N	Nivolumab in Arm N-I Dose Levels 1, 2 and 2b	Ipilimumab in Arm N-I Dose Levels 1, 2, and 2b
Dosing Schedule per Protocol	2 mg/kg every 2 weeks	1 or 3 mg/kg every 3 weeks for 4 doses followed by 3 mg/kg every 2 weeks  OR  Maximum tolerable dose identified in escalation phase.	1 or 3 mg/kg every 3 weeks for 4 doses
Dose	Dose (mg/kg) is defined as the minimum of [vial strength (mg/mL)*total volume infused (mL)]/most recent weight (kg) and nominal dose (mg/kg)*total volume infused (mL) /total volume prepared (mL)	Dose (mg/kg) is defined as the minimum of [vial strength (mg/mL)*total volume infused (mL)]/most recent weight (kg) and nominal dose (mg/kg)*total volume infused (mL) /total volume prepared (mL)	Dose (mg/kg) is defined as the minimum of [vial strength (mg/mL)*total volume infused (mL)]/most recent weight (kg) and nominal dose (mg/kg)*total volume infused (mL) /total volume prepared (mL)
Cumulative Dose	Cum Dose (mg/kg) is the sum of the doses administered to a subjects.	Cum Dose (mg/kg) is the sum of the doses administered to a subjects.	Cum Dose (mg/kg) is the sum of the doses administered to a subjects.
Dose Intensity (%)	7x Cum dose/(Last dose date - Start dose date + 14)	For Combo phase (the first two cycles): 7x Cum dose in Combo phase / (Last dose date in Combo phase - Start dose date + 21)  For Mono phase (cycle 3 and beyond): 7x Cum dose in Mono phase / (Last dose date - Start dose date in Mono phase + 14)	7x Cum dose/(Last dose date - Start dose date + 21)
Relative Dose Intensity (%)	Cum dose / [(Last dose date - Start dose date + 14) x 3/14] x 100	Cum dose / [(3 or 1) x (Last dose date - Start dose date + 21)/21] x 100, if the last dose is in Combo phase  Cum dose / [(3 or 1) x 4 + 3 x (Last dose date - 84 + 14)/14] x 100, if the last dose is in Mono phase	Cum dose / [(3 or 1) x (Last dose date - Start dose date + 21)/21] x 100, if subjects don't have re-exposure.  Cum dose / [(3 or 1) x (Last dose date - Gap - Start dose date + 21)/21] x 100, where Gap is between stop date and re-exposure date for subjects with re-exposure.
Duration of Treatment	Last dose date - Start dose date + 1	Last dose date - Start dose date + 1	Last dose date - Start dose date + 1

Volume infused, volume prepared, and weight are collected on the CRF. Nominal nivolumab dose collected in IVRS.  $i = 1, 2, \dots, N$ , where  $N =$  number of infusions. Cycle Duration ( $N$ ) = 3 weeks for nominal 1 or 3 mg/kg nivolumab doses and 2 weeks for nominal 3

mg/kg. Intended dose per week is .33 or 1 mg/kg for nominal 1 or 3 mg/kg nivolumab doses and 1.5 mg/kg nivolumab doses. If different from the above dosing, the MTD will be used for ARM N-I.

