## 2.4 Protocol Amendments

All protocol amendments related to the SCLC cohort are included below.

Amendments 1-5 did not affect the statistical analysis.

Amendment 07 is to update pharmacogenetics blood sample to include all current and future tumor types.

Amendment 08 is to add nivolumab 3 mg/kg in combination with ipilimumab 1 mg/kg to the dose levels being investigated in study CA209-032, and to add an optional external evaluation of CT or MRI scans.

Amendment 09 includes:

- SCLC: arms nivolumab 3 mg/kg and nivolumab 1 mg/kg combined with ipilimumab 3 mg/kg, increase sample size.
- Updates to Blinded Independent Central Review (BICR) information.
- Allowing brain radiation prior to crossover.
- Allowing retreatment upon PD for patients with long lasting PR or CR and who had treatment held by investigator.
- For the combination arm, subjects who meet discontinuation criteria will be allowed to continue with nivolumab treatment should the study related toxicities be attributed to ipilimumab. Ipilimumab would be discontinued.
- Updates to Primary, Secondary ██████████ Objectives.
- Updates to Discontinuation criteria to include Grade 4 lymphocytopenia.
- Updates to EQ-5D collection.

Amendment 10 includes:

- Clarification regarding PK/immunogenicity sampling and pregnancy test was added.
- Safety assessments in all indications and treatment cohorts is harmonized: D4 W2 and W5 safety assessments are deleted from the NI cohorts consistent with nivolumab monotherapy.
- For options of treatment beyond progression and crossover to NI combination arm, specification of unequivocal disease progression based on non-target lesions only is added.
- Specification of response to platinum-based therapy in SCLC is added to appendices.
- For SCLC expansion cohort, clarification of stratified randomization is added.
- For subjects from NI combination who undergo a re-exposure if they achieved an initial objective response (PR or CR) or stable disease of > 3 months and had a subsequent documented progression, an option to continue treatment with nivolumab monotherapy if ipilimumab treatment was sopped due to toxicity is added.

Amendment 11 includes:

- Clarification regarding the local lab assessment timing was added.
- For SCLC expansion cohort, exact language regarding number of prior treatment lines added for consistency with Section 3.1.5 of the protocol and the study synopsis.

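### The Arm N-I nivolumab relative dose intensity formula for a last dose in the mono phase omits the start date, and the SCLC table removes the re-exposure gap for ipilimumab only

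*SAP*

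**What the plan says.** Both SAPs define RDI in Table 7.4.1-1 (Section 7.4.1) as cumulative dose divided by planned dose over the treatment period. The planned Arm N-I nivolumab schedule in the same table is "1 or 3 mg/kg every 3 weeks for 4 doses followed by 3 mg/kg every 2 weeks".

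The Arm N-I nivolumab cell has two branches:

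- Last dose in the combination phase: the denominator uses "Last dose date - Start dose date + 21)/21] x 100, if the last dose is in Combo phase", which is an elapsed time.
- Last dose in the mono phase: the denominator is four nominal combination doses plus "3 x (Last dose date - 84 + 14)/14] x 100, if the last dose is in Mono phase".

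Every other expression in the RDI row subtracts the start dose date. The mono-phase branch is the only one that does not, and it is the same in the general SAP (version 2.0) and the SCLC expansion SAP.

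For ipilimumab, the SCLC table adds a version for re-exposed subjects that subtracts a gap, "where Gap is between stop date and re-exposure date for subjects with re-exposure". Neither nivolumab column has such a term. The general SAP's table has no gap term in any column, so the inconsistency within one row is confined to the SCLC table.

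Section 2.4 of the SCLC SAP describes re-exposure of combination subjects, and retreatment at progression after treatment was held for a lasting response. It also records that in the combination arm "subjects who meet discontinuation criteria will be allowed to continue with nivolumab treatment should the study related toxicities be attributed to ipilimumab". It does not say when maintenance dosing then begins.

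Section 7.4.1 of both SAPs reports "Relative dose intensity (%) using the following categories" of <50%, 50 to <70%, 70 to <90%, 90 to <110% and ≥110%, with a by-subject listing.

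**The concern.** A percentage of planned dose needs elapsed time in its denominator. The mono-phase branch supplies a date. In SAS a date is the number of days since 1 January 1960, so for dosing in this trial's period the denominator becomes several thousand mg/kg, and all Arm N-I subjects who reach maintenance land in the lowest category.

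The missing nivolumab gap is a separate matter. Time off drug before re-exposure is counted as planned dosing for nivolumab but not for ipilimumab, so the two drugs given to one subject would be summarised on different bases.

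What is at stake is whether the exposure table and listing for the combination arms can be read, and whether two programmers would produce the same table. Safety is a secondary objective, and exposure is part of its context.

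**Working it through.** **Notation.** C = cumulative nivolumab dose (mg/kg); d = nominal combination dose (1 or 3 mg/kg); L = last dose date; S = start dose date. Doses and intervals come from Table 7.4.1-1. Calendar dates, gap lengths and switch times are assumptions for illustration.

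**1. The plan's own constant.** 4 doses x 21 days = 84 days. The offset is right for the planned schedule.

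**2. The formula as printed:** RDI = C / [4d + 3 x (L − 84 + 14)/14] x 100.

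Take d = 1 and four maintenance doses on schedule (days 84, 98, 112, 126), so C = 4 + 12 = 16. With L = 1 June 2016, SAS date 20606:

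- denominator = 4 + 3 x 20536/14 = 4404.6
- RDI = 16/4404.6 = 0.36%

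With ten maintenance doses (C = 34), the result is 0.77% for a start on 1 March 2016, 0.80% for a start in January 2014 and 0.74% for a start in January 2018.

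**3. With the start date subtracted:** RDI = C / [4d + 3 x (L − S − 84 + 14)/14] x 100.

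- Same subject, L − S = 126: 16/(4 + 3 x 56/14) = 16/16 = 100%.
- After 1, 5, 10 and 20 maintenance doses at d = 1: 7/7, 19/19, 34/34 and 64/64, all 100%. With d = 3 it is also 100%.
- A delay still lowers RDI. A 14-day delay in the combination phase, then ten maintenance doses: 34/37 = 91.9%.

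**4. Re-exposure without a gap term.** Four combination and ten maintenance doses, then g days off beyond the normal interval, then five maintenance doses: C = 4 + 45 = 49 and L − S = 280 + g. With the start date restored, the denominator is 49 + 3g/14.

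| g (days, assumed) | RDI without gap | RDI with gap removed |
|---|---|---|
| 90 | 49/68.3 = 71.8% | 100% |
| 180 | 49/87.6 = 56.0% | 100% |
| 365 | 49/127.2 = 38.5% | 100% |

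Arm N, using the 3 mg/kg per 14 days in its RDI cell: 26 doses, an assumed 182-day hold, then 13 doses gives 117/[(714 + 14) x 3/14] = 117/156 = 75%.

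**5. Re-exposure to the combination.** Four combination, ten maintenance, a gap, four combination and five maintenance doses, all on schedule: C = 4 + 30 + 4 + 15 = 53. With the gap removed but only one combination block credited, L − S − g = 364 and the denominator is 4 + 3 x 294/14 = 67, so RDI = 53/67 = 79%. Summed by block, (4 + 30) + (4 + 15) = 53, so RDI = 100%.

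**6. Meaning of the gap.** Two on-schedule ipilimumab blocks of four, with 1 mg/kg doses on days 0 to 63 and 363 to 426. If the gap starts at the last dose (300 days): 8/[(426 − 300 + 21)/21] = 8/7 = 114%. If one dosing interval is kept first (279 days): 8/8 = 100%.

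**7. Early maintenance (conditional).** Two combination doses at 1 mg/kg, then seven maintenance doses from day 42 (assumed): C = 2 + 21 = 23 and L − S = 126.

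- Fixed 4 and 84: 23/(4 + 3 x 56/14) = 23/16 = 144%.
- With n = 2 and 21 x 2 = 42: 23/(2 + 3 x 98/14) = 23/23 = 100%.

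**The case against.** The strongest reply is that the omission is an obvious slip. The other cells in the row show the intended quantity, a programmer would very likely insert the start date, and an RDI below 1% for every maintenance subject would be noticed at once. Reading the last dose date as days since first dose already gives 100% on schedule. That is persuasive about likely consequences, but the SAP does not define the term that way. Read as a study day counted from 1, it gives 97.0% after one maintenance dose and 99.4% after ten. The text is still wrong as written.

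A reader might also infer that the fixed 84 days is itself an error. The documents do not support that: it equals the planned combination phase, and RDI ought to fall when that phase is delayed. The 144% depends on maintenance starting at day 42, whereas Section 2.4 says only that nivolumab may continue. If nivolumab kept its planned schedule to day 84, the formula with the start date restored would give 100%. Likewise, the 114% for ipilimumab depends on what the stop date means, which the table does not define. These are points to clarify, not shown errors.

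Finally, it is tempting to infer that exposure-toxicity conclusions are compromised. No test, decision rule or primary endpoint in the plan uses RDI. Section 4.2 assesses safety primarily by treatment-related AEs leading to discontinuation in the first 12 weeks, and the SCLC SAP's Section 7.8 reports exposure-response work separately. This objection stands and limits the severity.

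**Conclusion.** Wrong as written, minor severity. The missing start date in the mono-phase nivolumab RDI is certain in both SAPs. Taken literally it gives values of about 0.4% to 0.8% in the examples above, where 100% is right, and puts every Arm N-I maintenance subject in the <50% category. The exact figures rest on the assumed calendar dates; the conclusion does not.

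The missing nivolumab gap in the SCLC table is also real, because the ipilimumab cell of the same row removes it. It affects only re-exposed subjects, whose number is unknown, and its size depends on the assumed gap (72%, 56% or 39% instead of 100% for 90, 180 or 365 days in Arm N-I).

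The early-maintenance point is conditional on a timing that this document does not give. The effect is limited to a descriptive exposure summary and listing; the primary comparison of ORR by BICR is untouched.

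**What to change.** 1. In Table 7.4.1-1 of both SAPs, change the mono-phase term to (L − S − 84 + 14)/14, with S the start dose date.
2. In the SCLC table, subtract the re-exposure gap in both nivolumab columns, as the ipilimumab column does.
3. Define the gap as the re-exposure date minus (last dose date before the gap + one dosing interval), so that the interval belonging to that dose is kept.
4. For subjects re-exposed to the combination, sum the planned dose by treatment block.
5. If maintenance can start before four combination doses have been given, replace 4 by the number of combination doses received, n, and 84 by 21 x n. If it cannot, say so and keep the constants.

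Do not instead charge all time before the first maintenance dose at the combination rate, because that hides delays. With four doses of 1 mg/kg, a 42-day hold and ten maintenance doses, that version gives 34/(126/21 + 30) = 34/36 = 94%. Item 1 gives 34/(4 + 3 x 182/14) = 34/43 = 79%, which puts the subject in a different reporting category.

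The cost is table wording and one derivation. The dosing dates are already needed for the exposure listing, so no new data are required.

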**PROTOCOL CA209032**

**VERSION # 2.0**

**TABLE 1: REVISION HISTORY**

Revision	Date	Revised By	Changes Made -- Reasons for the Change
1.0	07 OCT 2013		Original issue
2.0	26 FEB 2016		
Incorporates Amendments 08, 09, and 10.
 
Summary of changes:
 
Amendment 08 is to add nivolumab 3 mg/kg in combination with ipilimumab 1 mg/kg to the dose levels being investigated in study CA209-032, change the bladder cohort to a One Stage Design.
 
Amendment 09 includes:
 
 
• SCLC and Bladder: arms Nivo 3 mg/kg and Nivo 1/ Ipi 3 mg/kg, increase sample size.
 
• Updates to Blinded Independent Central Review (BICR) information
 
• Updates to Primary, Secondary [REDACTED] Objectives
 
 
Amendment 10 includes:
 
 
• Regimen NI2c was added for treatment of ovarian cancer.
 
• For subjects from NI combination who undergo a re-exposure if they achieved an initial objective response (PR or CR) or stable disease of > 3 months and had a subsequent documented progression, an option to continue treatment with nivolumab monotherapy if ipilimumab treatment was stopped due to toxicity is added. (see Section 2.4 for details)
 

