**Table 7.4.1-1: Study Therapy Parameter Definitions**

	Nivolumab in Arm N and Arm N-I Dose Level 2c	Nivolumab in Arm N-I Dose Levels 1, 2 and 2b	Ipilimumab in Arm N-I Dose Levels 1, 2, 2b, and 2c
Dosing Schedule per Protocol	3 mg/kg every 2 weeks	1 or 3 mg/kg every 3 weeks for 4 doses followed by 3 mg/kg every 2 weeks OR Maximum tolerable dose identified in escalation phase. MTD may differ by tumor type	1 or 3 mg/kg 3 weeks for 4 doses or 1mg/kg 6 weeks (2c)
Dose	Dose (mg/kg) is defined as the minimum of [vial strength (mg/mL) *total volume infused (mL)] /most recent weight (kg) and nominal dose (mg/kg) * total volume infused (mL) /total volume prepared (mL)	Dose (mg/kg) is defined as the minimum of [vial strength (mg/mL) *total volume infused (mL)] /most recent weight (kg) and nominal dose (mg/kg) * total volume infused (mL) /total volume prepared (mL)	Dose (mg/kg) is defined as the minimum of [vial strength (mg/mL) *total volume infused (mL)] /most recent weight (kg) and nominal dose (mg/kg) * total volume infused (mL) /total volume prepared (mL)
Cumulative Dose	Cum Dose (mg/kg) is the sum of the doses administered to a subject.	Cum Dose (mg/kg) is the sum of the doses administered to a subject.	Cum Dose (mg/kg) is the sum of the doses administered to a subject.
Dose Intensity (%)	7x Cum dose/(Last dose date - Start dose date + 14)	For Combo phase (the first two cycles): 7x Cum dose in Combo phase / (Last dose date in Combo phase - Start dose date + 21) For Mono phase (cycle 3 and beyond): 7x Cum dose in Mono phase / (Last dose date - Start dose date in Mono phase + 14)	7 x Cum dose/(Last dose date - Start dose date + 21) For 2c: 7 x Cum dose/(Last dose date - Start dose date + 42)
Relative Dose Intensity (%)	Cum dose /[(Last dose date - Start dose date + 14) x 3/14] x 100	Cum dose/[(3 or 1) x (Last dose date - Start dose date + 21)/21] x 100, if the last dose is in Combo phase Cum dose/[(3 or 1) x 4 + 3 x (Last dose date - 84 + 14)/14] x 100, if the last dose is in Mono phase	Cum dose/[(3 or 1) x (Last dose date - Start dose date + 21)/21] x 100 For 2c: Cum dose/[(1) x (Last dose date - Start dose date + 42)/42] x 100
Duration of Treatment	Last dose date - Start dose date +1	Last dose date - Start dose date +1	Last dose date - Start dose date +1

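### Ipilimumab relative dose intensity is mis-specified for re-exposed subjects: SAP v2.0 has no gap term, and the SCLC expansion SAP starts its gap at an undefined stop date

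*SAP*

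**What the plan says.** Both SAPs define study therapy parameters in a Table 7.4.1-1. This point concerns the ipilimumab column.

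- **SAP v2.0.** RDI at Dose Levels 1, 2 and 2b is "Cum dose/[(3 or 1) x (Last dose date - Start dose date + 21)/21] x 100". Dose Level 2c uses the same form with 42 days. There is no separate rule for re-exposure, yet the revision history lists Amendment 10 as incorporated, and that amendment concerns subjects "who undergo a re-exposure if they achieved an initial objective response (PR or CR) or stable disease" and then progressed.
- **SCLC expansion SAP.** The cell has two branches. The v2.0 form applies "Last dose date - Start dose date + 21)/21] x 100, if subjects don't have re-exposure". For all others the formula is "Cum dose / [(3 or 1) x (Last dose date - Gap - Start dose date + 21)/21] x 100". The subtracted term is explained only in these words: "where Gap is between stop date and re-exposure date for subjects with re-exposure". The term stop date is not defined in the readable text, although the same cell uses last dose date and start dose date. The Dose Intensity row of that column has no gap term.
- **Schedule and reporting.** The expansion SAP gives the ipilimumab schedule as "1 or 3 mg/kg every 3 weeks for 4 doses". Its section 7.4.1 summarises "Relative dose intensity (%) using the following categories: <50%, 50 - <70%; 70 - <90%; 90 - <110%; ≥110". SAP v2.0 section 7.4.1 uses the same bands.

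**The concern.** RDI should be 100% when every dose is given in full and on time. The +21 in the formula credits the interval that belongs to the final dose of a course. A subject with two courses needs that credit twice, and the time between courses should not count as planned dosing time. SAP v2.0 leaves the between-course time in. The expansion SAP tries to remove it, but the result depends on where the gap starts, and the table does not say.

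What is at stake is the description of ipilimumab delivery in re-exposed subjects. A fully compliant subject can be placed in almost any reporting band, depending on which SAP is applied and how a programmer reads one term. SAP v2.0 also describes the SCLC expansion cohorts (sections 2.1, 5 and 7.5.1.1), so the two tables can give different values for the same subject.

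**Working it through.** **Inputs.** The 21-day interval, the 4-dose course, the formulas and the bands come from the two tables and section 7.4.1. The documents give neither the number of ipilimumab doses on re-exposure nor the length of the interval. I assume 1 to 4 re-exposure doses, and G = 90, 180 or 365 days from the last first-course dose to the first re-exposure dose. The SAPs state no RDI value to reproduce.

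**Check of the base formula.** For k on-schedule doses without re-exposure, the denominator is [21(k−1) + 21]/21 = k, so RDI = 100% for k = 1, 2, 3 and 4. Any departure below therefore comes from the handling of re-exposure.

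**SAP v2.0, 4+4 doses on schedule.** First-course doses fall on days 0, 21, 42 and 63. Re-exposure starts on day 63 + G, and the last dose is on day 126 + G. RDI = 8 / [(126 + G + 21)/21] = 168/(147 + G).

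| G (days, assumed) | Calculation | RDI | Band |
|---|---|---|---|
| 21 | 168/168 | 100% | 90 to <110% |
| 90 | 168/237 | 70.9% | 70 to <90% |
| 180 | 168/327 | 51.4% | 50 to <70% |
| 365 | 168/512 | 32.8% | <50% |

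Any G above 21 gives less than 100%. With 4+1 doses the last dose is on day 63 + G, and RDI = 105/(84 + G), which is 60.3%, 39.8% and 23.4% at 90, 180 and 365 days.

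**Expansion SAP, same 4+4 subject.** Let the stop date be s days after the last first-course dose. Then Gap = G − s, the denominator is (126 + G − (G − s) + 21)/21 = (147 + s)/21, and RDI = 168/(147 + s). G cancels and only s matters.

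| Reading of stop date | s | RDI | Band |
|---|---|---|---|
| Last first-course ipilimumab dose | 0 | 168/147 = 114.3% | ≥110% |
| That dose plus 21 days | 21 | 168/168 = 100% | 90 to <110% |
| Later stop of all therapy (assumed 90 days) | 90 | 168/237 = 70.9% | 70 to <90% |
| Later stop of all therapy (assumed 180 days) | 180 | 168/327 = 51.4% | 50 to <70% |

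With s = 0 and n on-schedule doses in total, the denominator is n − 1 and RDI = n/(n−1). After a full first course: 4+1 gives 5/4 = 125%, 4+2 gives 6/5 = 120%, 4+3 gives 7/6 = 116.7% and 4+4 gives 8/7 = 114.3%.

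**Dose Intensity against RDI in the expansion SAP.** Dose Intensity is 7 × cumulative dose / (last − start + 21), without a gap. At 3 mg/kg, 4+4 doses total 24 mg/kg. With G = 365, 7 × 24/512 = 0.328 mg/kg per week, or 32.8% of the scheduled 1 mg/kg per week (3 mg/kg every 3 weeks). The next row of the column reports 114.3% or 100% for the same subject under the first two readings.

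**Check of the fix.** Summing (last − first + 21)/21 over courses gives (63 + 21)/21 + (63 + 21)/21 = 8, so RDI = 8/8 = 100%. This equals setting s = 21. It returns 100% for every combination of 1 to 4 and 1 to 4 doses, whatever G is.

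**The case against.** The strongest objection is that the expansion SAP contains an undefined term, not a demonstrated arithmetic error. A reader might infer that everyone re-exposed on schedule is reported as overdosed, at 114% to 200%. The document does not support that, for three reasons.

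- Stop date may mean something other than the last dose, since the cell already has a term for the last dose, and one plausible reading gives exactly 100%. The lost-interval reading has some support: section 7.4.1 uses the last dose date as the event for subjects off therapy. That favours the reading but does not settle it.
- The 200% end needs a single ipilimumab dose in each course (2/1).
- Even with s = 0, small slippage changes the band. One day late in each of the six within-course intervals of a 4+4 subject gives 168/(147 + 6) = 109.8%, below the top band, and section 7.4.2.1 counts no dose as delayed until it is 4 days late.

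A reader might also infer that this distorts the comparison of response rates. It does not. Re-exposure under Amendment 10 follows documented progression, and section 4.1.1 closes the best-overall-response window at progression.

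Duration of treatment also spans the gap, but last dose minus first dose plus one is an explicit definition. Summing it by course would be a preference, and no change is asked for.

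Finally, the expansion SAP is the later document and did add a gap rule. That does not repair SAP v2.0, whose table also covers the other tumour types. The v2.0 percentages depend on assumed intervals, but their direction does not.

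**Conclusion.** The concern holds in a limited form. In SAP v2.0 the formula, followed as written, understates RDI for every compliant re-exposed subject whose interval exceeds 21 days (42 days for Dose Level 2c). In the expansion SAP the value cannot be determined until stop date is defined: the readings examined put one 4+4 subject anywhere from 51.4% to 114.3%, across four of the five bands. The expansion SAP's Dose Intensity and RDI rows also use different time bases. The figures rest on exact on-schedule dosing, on 1 to 4 re-exposure doses and on the intervals shown. The number of re-exposed subjects is not stated. The consequence is confined to descriptive exposure summaries and listings.

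**What to change.** In the ipilimumab column of Table 7.4.1-1 in both SAPs, define the RDI denominator as planned dose × the sum over courses of (last dose date − first dose date + 21)/21, with 42 in place of 21 for Dose Level 2c. Equivalently, keep the gap form and state that Gap starts 21 days (42 for 2c) after the last ipilimumab dose of the first course. Use the same summed time in days in the Dose Intensity row, so that the two rows agree. The cost is a few formula lines in each SAP and minor reprogramming. No new data are needed.
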